5.3 SCREENING FOR ELIGIBILITY

Participants must have documented Type 2 Diabetes Mellitus and CHF with LVSD. Post consent, screening bloods will be performed to ensure renal function and HbA1c meet the inclusion criteria. Blood pressure and heart rate will also be measured. Women of child bearing potential will have a pregnancy test. Participants will be consented prior to screening and a screening log will be maintained.

5.4 INELIGIBLE AND NON-RECRUITED PARTICIPANTS

The reason(s) for ineligibility will be explained to participants and any questions they have will be answered. They will be thanked for their participation in screening and any relevant information from this will be added to their hospital notes and be communicated to their GP and consultant, where the participant consents for this to happen.

5.5 RANDOMISATION

5.5.1 Randomisation

After successful screening for eligibility and safety, participants will be randomised to either empagliflozin 25mg/ placebo or placebo/empagliflozin 25 mg in a double blind fashion in this crossover study.

The double blind medication (empagliflozin or placebo) will be prepared, packaged and labelled by Tayside Pharmaceuticals. Randomisation will be carried out by Tayside Pharmaceuticals, using block randomisation using a validated randomisation programme, and will securely backup both the randomisation seed and the randomisation allocation.

The Clinical Trials Pharmacy, Ninewells Hospital will be provided with a copy of the randomisation allocation for the purposes of 24h emergency unblinding.

5.5.2 Treatment Allocation

Participants will be given blinded medication. At the randomisation visit they will be dosed with either empagliflozin 25mg (6 weeks) or matched placebo (6 weeks) to continue once daily, with a 2-week washout period between each arm. Participants and their bloods (including U&Es and LFTs, FBC) will be monitored as per trial schedule and medication stopped if concerns arise. If trial drug needs to be stopped

due to intolerance or adverse events, they will remain in the trial in order to do an "intention to treat" analysis. They will be invited to attend all future trial visits.

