The intent of this proposed trial is to obtain data that might be relevant to the design of future studies in which SGLT2 inhibitors may be considered as an adjunctive agent to loop diuretics in this vulnerable participant group. There is currently no data on combining SGLT2 inhibitors and diuretics, which is why this combination is not recommended at this point in time. However, it should be noted that in EMPA-REG 43% of participants were on loop diuretics. Since HF and T2D are frequent comorbidities, it is possible that physicians may find participants requiring both SGLT2 inhibitor therapy and furosemide concurrently. Only by trialling this, can these fundamental issues be addressed and, perhaps, inspire a change in practise.

We will recruit diabetic HF participants taking stable doses of furosemide, or, alternative loop diuretics, with eGFR greater than 45ml/min. Whilst SmPC states that empagliflozin should not be administered with an eGFR < 60 ml/min, EMPA-REG recruited participants with an inclusion criteria of eGFR ≥ 30 ml/min. 15 Within the total number of participants, n = 1819 (25%), with an EGFR < 60 mls/min, 1,212 were randomised to empagliflozin¹⁵. There was no reported increase in renal adverse events (acute kidney injury or hyperkalaemia) in those with eGFR < 60 mls/min regardless of whether the patients had impaired kidney function at baseline. Further analysis in the EMPA-REG renal outcome, demonstrated that in patients with T2D at high risk for cardiovascular events, those who received empagliflozin in addition to standard care had a significantly lower risk of microvascular outcome events than did those receiving placebo, a difference that was driven by a lower risk of progression of kidney disease (as defined by incident or worsening nephropathy).32 Furthermore the Dapa-HF trial (clinical trials.gov identifier NCT03036124) will set an inclusion of eGFR > 30mls/min to further evaluate the effect of dapagliflozin on the incidence of worsening HF or cardiovascular death in patients with CHF.

As there will be administration of intravenous furosemide of half the participant's usual daily dose with the RECEDE-CHF protocol, an eGFR ≥ 45 ml/min will be taken as a cut off for inclusion.

This trial will, with careful monitoring, begin the process of uncovering the unrealised potential of this new class of drug, and for the reasons given above, it is poised to become the 2nd line anti-diabetic agent of choice in HF participants.

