6 INVESTIGATIONAL MEDICINAL PRODUCT

6.1 TRIAL DRUG

6.1.1 Trial Drug Identification

Jardiance tablet (25mg) over-encapsulated in hard gelatine capsule shell.

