6.8 DISCONTINUATION

The trial medication will be discontinued due to safety and/or tolerability in the following circumstances:

- Participant becomes pregnant
- LFTs rise to greater than twice the normal range
- Participant develops symptoms of NYHA class IV heart failure
- Participant has vomiting and diarrhoea for 48 hours and volume depletion is suspected
- Participant develops symptomatic postural hypotension
- Participant develops signs of vulvovaginitis, balanitis and related genital infections or urinary tract infections which do not respond to treatment.
- Participant has suspected or diagnosed Diabetic Ketoacidosis
- Participant develops a sustained eGFR < 45 mls/min despite alteration of dose of furosemide or alternative loop diuretic

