18 APPENDIX 2: TRIAL DAY TIMELINE

- 2 days pre-trial day: 2gram sodium and 2L/day controlled diet (food diary)
- 1 day: 24 urinary collection

Interval (minutes)	Urine		Blood	
- 30				Arrives fasted. 2 x cannula sited
- 15				15mls/kg oral water load over 15 minutes
0				
+ 30	Void urine. Water intake equal to urine volume.			
+ 60	Void urine. Water intake equal to urine volume			
+ 90	Void urine. Water intake equal to urine volume.			
+ 105			Bloods (serum B1) for U&Es & osmolality	
+ 120	Void urine. Water intake equal to urine volume. Collect urine (urine B1) for volume, sodium, creatinine & osmolality.	B1 (90-120 mins)		
+ 135			Bloods (serum B2) for U&Es & osmolality	
+ 150	Void urine. Water intake equal to urine volume. Collect urine (urine B2) for volume, sodium, creatinine & osmolality	B2 (120-150 mins)		IMP administered: Oral tablet (empagliflozin 25mg or placebo)

+ 165		D1 (150-180 mins)	Bloods (serum D1) for U&Es & osmolality	
+ 180	Void urine. Water intake equal to urine volume. Collect urine for volume, sodium, creatinine & osmolality			
+ 195		D2 (180-210 mins)	Bloods (serum D2) for U&Es & osmolality	
+ 210	Void urine. Water intake equal to urine volume. Collect urine for volume, sodium, creatinine & osmolality			IV Frusemide administered: half participant's screening dose
+ 225		F1 (210 – 240 mins)	Bloods (serum F1) for U&Es & osmolality	
+ 240	Void urine. Water intake equal to urine volume. Collect urine for volume, sodium, creatinine & osmolality			
+ 255		F2 (240-270 mins)	Bloods (serum F2) for U&Es & osmolality	
+ 270	Collect urine for volume, sodium, creatinine & osmolality.			END OF STUDY PERIOD

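### A stop for sustained eGFR below 45 covers only the trial capsule and leaves the test-day IV furosemide scheduled with no hold rule (minor)

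*Protocol*

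**What the plan says.** Protocol 6.8 begins "The trial medication will be discontinued due to safety and/or tolerability in the following circumstances" and lists eight criteria. One is renal: "Participant develops a sustained eGFR < 45 mls/min despite alteration of dose of furosemide or alternative loop diuretic". Two concern volume and blood pressure: "Participant has vomiting and diarrhoea for 48 hours and volume depletion is suspected", and symptomatic postural hypotension. Section 6.1.1 identifies the trial drug as "Jardiance tablet (25mg) over-encapsulated in hard gelatine capsule shell", and 6.2.1 gives the placebo capsule as comparator. Furosemide is neither.

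Under 5.5.2, a participant whose trial drug is stopped for intolerance or an adverse event stays in the trial for the intention-to-treat analysis: "They will be invited to attend all future trial visits". Section 5.5.4 likewise encourages those who come off trial drug to keep attending for the outcome measures.

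The renal test is held at visits 3, 5, 7 and 9 (SAP Table 1). At +210 minutes Appendix 2 has "IV Frusemide administered: half participant's screening dose". Section 3.2.3 also gives the bolus at every test. Neither place makes it conditional on eGFR, blood pressure or volume status.

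Section 1.2 explains the entry limit: "As there will be administration of intravenous furosemide of half the participant's usual daily dose", it says, "an eGFR ≥ 45 ml/min will be taken as a cut off for inclusion".

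**The concern.** The protocol chose 45 ml/min with the IV bolus in mind, and 6.8 uses the same figure as a stopping criterion. But the stop removes the capsule and leaves the bolus. Followed as written, the plan would give IV furosemide to someone who has fallen below the limit set because of that furosemide, and whose eGFR stayed low after the loop diuretic dose was altered.

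A clinician may well hold the bolus, but nothing says so. Section 14.2 allows a departure from the protocol without sponsor agreement only to remove an immediate hazard. A stable, symptom-free eGFR just below 45 may not be seen as one, so a prudent hold could itself become a deviation that needs agreement.

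**Working it through.** The plan gives no figure on this point to reproduce. The check compares the texts and then counts scheduled boluses.

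**1. What a stop reaches.** 6.8 covers trial medication, and 6.1.1 and 6.2.1 limit that to the capsule. A stop therefore removes the capsule at +150 minutes in Appendix 2. Nothing removes the furosemide at +210 minutes.

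**2. Whether the participant is still at the test.** 5.5.2 and 5.5.4 keep a stopped participant attending, with no exception for test days. The only visit stated to omit the renal test is the early discontinuation visit in 5.5.4, which is for participants who withdraw. That section treats them separately from those who come off trial drug only.

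**3. How many boluses remain.** Inputs: renal tests at visits 3, 5, 7 and 9; safety bloods at visits 3, 5, 6, 7 and 9 after randomisation; visits 4 and 8 by telephone (Appendix 1). A sustained fall despite a dose alteration needs at least two low results with the alteration between them.

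| Route to the stop | Tests left | Boluses still scheduled |
|---|---|---|
| Low at visit 3, still low at visit 5 | 7, 9 | 2 |
| Low at visit 5, still low at visit 6 | 7, 9 | 2 |
| Low at visit 6, still low at visit 7 | 9 | 1 |
| Unscheduled bloods lead to a stop between visits 3 and 5 | 5, 7, 9 | 3 |

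These are maxima. They assume full attendance, no clinical hold, and an eGFR that stays below 45. The protocol does not say whether a stop in period 1 carries into period 2, but the count is the same either way, because visits 7 and 9 schedule the bolus regardless.

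**4. The two volume-related criteria.** Nominal test days are 3, 6 × 7 = 42, 9 × 7 + 3 = 66 and 15 × 7 = 105. The gaps are 42 − 3 = 39, 66 − 42 = 24 and 105 − 66 = 39 days. A short illness need not be present at the next test, so these criteria matter only if unresolved on the day.

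**5. Monitoring after the bolus.** The test ends at +270, which is 270 − 210 = 60 minutes after the bolus. With blood pressure taken about every 60 minutes, that is about one reading.

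**6. Data lost if a bolus is held.** There are 6 timed collections (B1, B2, D1, D2, F1, F2), of which 2 (F1, F2) follow furosemide. The primary endpoint in SAP 5.4 is the 24-hour collection, which is complete before the test starts.

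**The case against.** **The test is written for someone on trial drug.** The same timeline gives the capsule, so it cannot be run unchanged after a stop. That is true, but the stop itself settles the capsule. No text settles the bolus.

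**The early discontinuation visit covers this.** Section 5.5.4 omits the renal test there and refers to 6.8 for reasons to stop. But it distinguishes withdrawing from the trial from coming off trial drug, and it offers that visit to the first group. The visit 9 footnote in Appendix 1, which has all procedures done as at the final visit, does not help either side: 5.5.4 calls week 15 final, while Appendix 1 labels visit 10 final, and visit 10 has no renal test.

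**The limit of 45 concerns the combination.** Section 1.2 weighs how low an eGFR is acceptable for empagliflozin when IV furosemide is added. After a stop, empagliflozin is gone, and 6.8 does not stop the participant's own loop diuretic. This stands in part. The documents do not show that the bolus alone is hazardous below 45, and the point should not be read as saying so.

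**Safeguards exist.** The oral loop diuretic is withheld that morning, urine volume is replaced with water up to +240 minutes, heart rate is displayed continuously, and vital signs, safety bloods and questions about postural hypotension are scheduled at these visits. Section 10.2 directs the investigator to treat adverse events on medical judgement, and 10.8 and 14.2 allow action against an immediate hazard. For unresolved volume depletion or symptomatic hypotension this is largely an answer. For a stable low eGFR it is not.

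**Stronger readings to avoid.** A reader might infer that an eGFR stop should bar the bolus for good. Section 1.2 describes the early eGFR fall seen with dapagliflozin as reversible, so a permanent bar is not supported. A reader might also infer from Appendix 2 that the bolus would be too large after a diuretic reduction. But 6.8 gives neither the size nor the direction of the alteration, and a participant whose bolus is held receives none.

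**Conclusion.** The gap is real on the text, and minor. It rests mainly on one of the eight criteria in 6.8, the sustained low eGFR. Two others (suspected volume depletion and symptomatic postural hypotension) belong in the same rule for completeness, although current safeguards largely handle them.

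The exposure is typically at most 2 further boluses per affected participant on scheduled bloods, and 3 only if unscheduled bloods led to a stop between visits 3 and 5. How many participants would be affected cannot be estimated from the documents; the number is probably small. The conclusion assumes that staff follow the text as written and that a stable eGFR below 45 is not treated as an immediate hazard under 14.2. It does not assume that harm would occur.

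**What to change.** Add to 3.2.3 and Appendix 2 a rule to this effect:

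> IV furosemide is not given on a test day if the participant has been stopped under 6.8 for eGFR and the most recent eGFR is below 45 ml/min; it may be given again once eGFR is 45 ml/min or above. It is also not given if suspected volume depletion or symptomatic postural hypotension is present that day. The 24-hour collection, bloods and safety checks go ahead.

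Report held boluses by treatment and reason, in line with what 5.5.4 already asks for withdrawals.

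**Cost.** No new visit, sample or test is needed, and the 24-hour endpoint in SAP 5.4 is kept. For a held visit, F1 and F2 are lost (2 of 6 timed collections, or all 6 if the team omits the whole test). The Professional Summary words the primary endpoint as the response to furosemide, so under that wording the visit's value is lost too. Such losses may be related to treatment, so missing at random (Protocol 9.3, SAP 7.4) should not be assumed for them. A standard repeated measures ANOVA of the renal tests (SAP 9.2) needs complete sets and may drop that participant.

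The two descriptions of the bolus dose, half the screening dose in Appendix 2 and half the total daily dose in 3.2.3, should be reconciled as a separate point.

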5.5.3 Emergency Unblinding Procedures

A clinician familiar with the research (and named on the delegation log) will be available each workday for contact by all participants. This will include the CI, the PI/ a research fellow based within the Division of Cardiovascular and Diabetes Medicine Department at Ninewells Hospital.

Any other clinician who sees participants during trial participation will be free to stop the trial drug if they feel it is clinically indicated and be asked to inform the trial team. The Clinical Trials Pharmacy, Ninewells Hospital will be provided with a copy of the randomisation allocation for the purposes of 24h emergency unblinding. During office hours the Clinical Trial Pharmacy, Ninewells Hospital, should be contacted if unblinding is required, out of hours the On-call Pharmacist should be contacted via Ninewells Hospital switchboard.

5.5.4 Withdrawal procedures

Participants are free to withdraw from the trial at any time. Although a participant is not obliged to give reason(s) for withdrawing prematurely, if the participant appears lost to follow up, the CI will make a **reasonable** effort to ascertain the reason(s), while fully respecting the individual's rights, and will demonstrate that everything possible was done in an attempt to find any participant lost to follow-up. Those lost to follow-up or withdrawn will be identified and a descriptive analysis of them provided, including the reasons for their loss and its relationship to treatment and outcome.

Participants who withdraw will be replaced if possible within the trial time frame. Those that withdraw from trial drug will be encouraged to attend future trial visits and where possible the final visit for the outcome measures. Participants who withdraw will be invited to a final 'early discontinuation' visit. At this visit, the tests that would be taken at week 15 the final study visit, including vital signs and blood samples for NT-proBNP, serum sodium, osmolality and creatinine, for safety, research and genetic bloods (without undergoing the detailed renal physiological testing), to allow the investigators to obtain further information on the safety of the drug.

If withdrawal is due to an adverse event (AE), contact will be maintained by the PI or delegate with the individual to ensure resolution of the AE; this will also be logged in the AE log and participant's hospital case notes.

Reasons for treatment discontinuation due to safety and/or tolerability are listed in section 6.8. There is an increased risk of hypoglycaemia, as discussed in section 10.2

Participants' anti-hyperglycaemic medications may be adjusted as deemed necessary by a trial doctor, local NHS clinic or GP in order to achieve an appropriate individualised glycaemic control according to local guidelines without them having to stop the trial medication. Medications will be reconciled at all 9 patient visits (see Appendix 1) so that documentation can be made of any changes to participants' other regular medication. Where medication has been adjusted, the Emergency Care Summary, an online patient record used to document repeat and acute prescriptions will be used to clarify the start and stopping date for any medication changes. Changes made by Hospital based doctors will be seen on Medical documentation and clinic letters. If clarification is required for changes made in the community, then the GP Practice may be contacted directly to clarify the date and indication for change.

6 INVESTIGATIONAL MEDICINAL PRODUCT

6.1 TRIAL DRUG

6.1.1 Trial Drug Identification

Jardiance tablet (25mg) over-encapsulated in hard gelatine capsule shell.

6.1.2 Trial Drug Manufacturer

Tayside Pharmaceuticals, Ninewells Hospital, Dundee.

6.1.3 Marketing Authorisation Holder

Not applicable. IMP dossier to be formulated by Tayside Pharmaceuticals

6.1.4 Labelling and Packaging

Tayside Pharmaceuticals, Ninewells Hospital, Dundee.

6.1.5 Storage

IMP will be stored in the Clinical Trial Pharmacy (Ninewells Hospital, Dundee). IMP accountability logs will be held in the Pharmacy Site File (PSF).

6.1.6 IMP Safety Information

The Summary of Product Characteristics (SmPC) will be held in the PSF and TMF. Section 4.8 will be used to assess the causality of any adverse event in relation to the IMP. The CI will check at least annually for any changes to the SmPC. Where changes to Section 4.8 impact on the assessment of causality of adverse events, the new version of the SmPC will be submitted as an amendment prior to being used as reference safety information (RSI) and the updated SmPC will be provided to Pharmacy.

Common side effects of empagliflozin include, increased urination and vaginal yeast infection. Women who take empagliflozin may get vaginal yeast infections hence participations will be encouraged to approach either the PI or the GP if they experience vaginal odour, white or yellowish vaginal discharge and/or vaginal itching. Increased urination may be reported by the participant in the absence of any infection. Less common side effects include, dehydration and subsequent acute kidney injury, ketoacidosis (which has been reported in the absence of hyperglycaemia), urinary tract infections, hepatic injury and for men taking empagliflozin, yeast infection of the penis.

6.1.7 Accountability procedures

These will be overseen by the Clinical Trials Pharmacist in the Clinical Trials Pharmacy Department (Ninewells Hospital) and will be documented in an Accountability Log held in the PSF. Accountability will be in compliance with TASC SOP 37.

6.2 TRIAL COMPARATOR

6.2.1 Comparator Identification

Hard gelatine capsule shell containing Microcrystalline Cellulose Ph. Eur.

6.2.2 Comparator Manufacturer

Tayside Pharmaceuticals, Ninewells Hospital, Dundee.

6.2.3 Labelling and Packaging

Tayside Pharmaceuticals, Ninewells Hospital, Dundee.

6.2.4 Storage

Drugs will be stored in the Clinical Trial Pharmacy (Ninewells Hospital).

6.3 DOSING REGIME

Participants will be given blinded medication. At the randomisation visit, they will be dosed with either oral empagliflozin 25mg OD or matched placebo to continue for 6 weeks, if tolerated. This will be followed by a two-week washout period. The participant will then cross over to be given either placebo or empagliflozin 25mg OD for a further 6 weeks.

No additional lifestyle restrictions will be imposed on the participant and we will ask them to carry on as normal except in the 48 hours preceding the renal physiological tests where we would request a 2gm sodium and 2L fluid/day controlled diet**DOSE CHANGES**

No dose change is planned in this trial. If the participant is taken off the trial, their GP and/or consultant will be informed of the reason for that.

6.5 PARTICIPANT COMPLIANCE

Compliance will be checked and documented using tablet counts at both trial visits during each arm. A telephone visit is scheduled for week 3 and week 12 where compliance will be checked verbally and participants will be advised by the research nurse or PI on the importance of correct compliance.

6.6 OVERDOSE

This is unlikely given the simple once daily dosing but there is no specific antidote.

In the event of an overdose, appropriate supportive treatment should be initiated as dictated by the participant's clinical status. The removal of empagliflozin by haemodialysis has not been studied.

Overdose with empagliflozin is rare, however it has been noted that there is an increased risk of hypoglycaemia when given with insulin and/or sulphonylureas. The majority of the hypoglycaemic events are mild (defined as not requiring any assistance). In the case of any overdose, the patient will be advised to stop the medication and the event will be reported. If symptomatic, the patient (or their carer) will be advised to take an oral glucose load (sugary drink, fruit etc.) and if necessary to seek medical attention at their GP or hospital.

